### **2.6.3 Windows for time points**

Statistical analysis will be based on the nominal visit which should follow schedule defined in protocol Section 1. Visits will not be windowed for analysis purposes, except for unscheduled visits in some cases as described in [Section 2.6.4](#).

### **2.6.4 Unscheduled visits**

In general, unscheduled visit measurements will not be included in the by-visit summaries, but will be used for computation of baseline and/or summaries of “any time” or “end of study” time points. If a scheduled post-baseline visit measurement of an efficacy parameter is missing, but an unscheduled visit value for the same parameter is available within 3 months (91 days) of scheduled 6-month or 12-month visit, the unscheduled visit value will be used to substitute the missing scheduled visit value before any missing data imputation algorithm is implemented. If the parameter is scheduled for evaluation every 3 months, a 45 day window will be used instead of 91 days. If two unscheduled visits qualify for missing scheduled visit value, the one closest in date to target visit date will be used. If these two unscheduled visits happened in the same distance to the target visit date with one before and one after, the one before the target visit date will be used. Laboratory, vital signs, ECG and pharmacodynamic parameters are collected at several times during a visit with respect to the infusion time, therefore a window for an unscheduled visit to substitute missing schedule values will not be considered. For ADA analyses, unscheduled visits will be included in the by-visit summaries.

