11.5.2.1 Primary efficacy analysis

The 2 primary efficacy endpoints (percentage change in spleen volume in MN from baseline to Week 52 [combined with change in SRS from baseline to Week 52 in the US only, and is referred to as the “combination spleen endpoint”]) and percentage change in DL_{CO} in percent predicted from baseline to 52 weeks) will be analyzed in the mITT population using the mixed model for repeated measures.

For percent change in DL_{CO} (% predicted) from baseline, the mixed model for repeated measures (MMRM) will include baseline DL_{CO} (% predicted), baseline age, treatment arm, study visit (Week 26, Week 52), and study visit by treatment arm interaction as covariates; have an unstructured variance-covariance matrix; and be fit using restricted maximum likelihood estimation. Comparisons between treatment arms will be made using least-square mean contrasts at the 52 week visit.

The analysis will include all DL_{CO} observations after baseline in the first 12 months of the study regardless of the treatment discontinuation status, with the exception that measurements made after the switch of treatment (eg, placebo patients switch to olipudase alfa after meeting the rescue criteria) will not be considered. For the primary analysis, missing data will not be imputed and will be assumed as Missing at Random (MAR).

Similar analyses will be performed for the spleen volume (MN) and the splenomegaly-related symptom score (SRS), when baseline value of the spleen volume (or SRS) will be used as covariate.

Descriptive assessment of MAR assumption and sensitivity analyses to assess the impact of missing data are described in the SAP.

Hypothesis tests will be 2-sided and adjusted for multiple comparisons to maintain a family-wise Type 1 error rate of 5%. The details of multiplicity adjustments are provided in [Section 11.5.4](#).

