## 2 STATISTICAL AND ANALYTICAL PROCEDURES

The PAP analysis will be performed after all patients have had the chance to complete the Week 52 assessments (ie, at the completion of the 52-week PAP treatment period) and will include a formal database lock, unblinding of the study treatment arms, and analyses of efficacy, safety, pharmacodynamic, and pharmacokinetic data. The study treatments will remain blinded to the Sponsor until completion of the PAP; the investigator and patients will remain blinded until the last patient completes the dose escalation period in the ETP period. A CSR will be prepared for the PAP analysis. The database will contain all visits, events or procedures that occurred up to a cutoff date - to be pre-defined as few days after the last patient finishes PAP, and the data will be cleaned to a pre-specified extent. This will include PAP evaluations for all patients randomized, but will also include evaluations in ETP for most patients.

A formal summary of data as a CSR during the ETP may be produced to support regulatory approval(s) and/or other submission/application requirement(s).

The final CSR will be prepared after all patients have completed all the study assessments at the completion of the ETP and will include a final database lock. Any difference in data from PAP CSR will be highlighted within the final CSR.

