## **2.4.5 Analyses of efficacy endpoints**

Efficacy data will be analyzed by randomized treatment group in mITT population at scheduled time point. The statistical analyses will compare olipudase alfa versus placebo within PAP; the difference between two treatment groups is calculated as olipudase alfa minus placebo.

Primary analyses period is 52 weeks.

Efficacy analyses will use mITT population unless specified otherwise. This will include patients who used rescue therapy, but their data after rescue will NOT be included in the analysis. Sensitivity analyses including data beyond rescue therapy may be undertaken if appropriate.

Baseline values are generally the latest value before the first infusion of the study drug, except for platelets and hemoglobin which are part of hematology parameters; for hematology parameter baseline definition, please refer to [Section 2.6.1](#).

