The MMRM assumes data missing-at-random (MAR) and will include all DLco observations except for measurements made after the initiation of rescue therapy. In addition, for patients who do not have Week 52 value available but have a PFT value measured after Week 38 infusion (eg, patients discontinuing the study or initiating rescue therapy after Week 38 but before Week 52 may have the PFT measurements available from early discontinuation visit or right before rescue therapy starts), these values will be used as Week 52 value for analysis purposes; Week 52 DLco will not be considered missing in such situations. This idea is based on the clinical concept that PFT measurements are similar within a 12-week period.

The percentage change in spleen volume (MN) and the change in the splenomegaly-related score (for US, SRS is part of primary endpoints) will be analyzed using an analogous MMRM model.

The summary plots of the LS means from the MMRM of the percentage change in DLco (% predicted), the percentage change in spleen volume (MN) and the change in the splenomegaly-related score from baseline up to Week 52 with 95% CIs will be provided.

Sensitivity analyses for the primary efficacy endpoints to support robustness of results will include the following:

1. The MMRM described above will be run using the per-protocol population. This analysis will demonstrate whether the results vary depending on the population analyzed.
2. The MMRM described above will exclude observations made after the initiation of rescue therapy. As a sensitivity analysis, the observations collected after the initiation of rescue therapy will be included in the MMRM; the treatment arm for rescued patients will remain

as randomized treatment.

The MMRM planned for the primary efficacy analysis assumes MAR. To assess the robustness of the primary results to that assumption a pattern mixture model will be used (see [Section 2.6.6](#) for details).

3. The MMRM planned for the primary efficacy analysis assumes multivariate normality. To assess the robustness of conclusions under this assumption, nonparametric testing method will be used: A Wilcoxon-Mann-Whitney (WMW) will be used to compare the primary efficacy endpoints; missing Week 52 data will be imputed using LOCF, excluding patients who initiate rescue therapy.

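### SAP 2.6.4 lets an unscheduled value from up to Week 65 stand in for a missing Week 52 DLco, spleen volume or liver volume, with no stop at the first ETP infusion (nominally Week 54)

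*SAP*

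**What the plan says.** SAP 2.6.4 substitutes an unscheduled value for a missing scheduled post-baseline efficacy value if "an unscheduled visit value for the same parameter is available within 3 months (91 days) of scheduled 6-month or 12-month visit". Use of a qualifying value is mandatory and comes before any imputation. If two values qualify, the closer one is taken; if they are equally distant "with one before and one after, the one before the target visit date will be used". Laboratory, vital signs, ECG and pharmacodynamic parameters are exempt. DLco, spleen volume and liver volume are not, and all three are 6-monthly (SAP 2.1.4.1 and 2.1.4.2), so the 91-day window applies to them.

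SAP 1.1 has placebo patients cross to olipudase alfa at the first ETP infusion; protocol 8.1.3.3 puts that at Week 54. SAP section 2 says the PAP database will hold the PAP evaluations "but will also include evaluations in ETP for most patients".

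On what enters the primary model, SAP 2.4.5.1 states that the MMRM "will include all DLco observations except for measurements made after the initiation of rescue therapy". SAP 2.4.5 sets the general scope: "The statistical analyses will compare olipudase alfa versus placebo within PAP". Protocol 11.5.2.1 is tighter. It takes DLco "observations after baseline in the first 12 months of the study regardless of the treatment discontinuation status", and says that "measurements made after the switch of treatment (eg, placebo patients switch to olipudase alfa after meeting the rescue criteria) will not be considered". It extends the same approach to spleen volume and SRS. For secondary endpoints, including liver volume, protocol 11.5.2.2 leaves missing-data handling to the SAP.

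**The concern.** The forward half of the window reaches well past the point at which the placebo arm stops being a placebo arm. Section 2.6.4 does not mention the ETP, the crossover or the end of the PAP. Crossover at ETP entry is not rescue, so the exclusion in 2.4.5.1 does not catch it. Read literally, a value taken on olipudase alfa could be analysed as a placebo Week 52 value for either primary endpoint or for the first secondary endpoint in the testing sequence.

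The protocol wording on the first 12 months and on switches of treatment came in with amended protocol 09. The SAP is based on amended protocol 11, and SAP 1.5, which lists departures from the protocol, does not list this one.

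The SAP also treats the same value in two ways. SAP 2.6.6 ends the on-treatment period at the day before the first ETP infusion, but only for the pattern-mixture sensitivity analysis. A late DLco value could enter the primary MMRM and yet be barred from that imputation model.

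The direction of bias is not fixed. Late placebo values shrink the contrast. Late active-arm values, with up to 13 more weeks on drug, could enlarge it.

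**Working it through.** **Plan's own figure.** SAP 1.3 assumes a DLco difference of 25, SD 20, 36 patients randomized 1:1, 11% without a Week 52 result and a two-sided 5% t-test. Evaluable patients: 36 × 0.89 = 32.04, or 16 per arm. Noncentral-t power is 92.8%, against the stated 93%. For spleen volume (difference 30, SD 11.8) it exceeds 99.9%, against the stated 99%.

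**Dates.**
- 91 / 7 = 13 weeks, so the window closes at Week 52 + 13 = Week 65.
- The first ETP infusion is nominally 14 days after Week 52. Forward days after crossover: 91 − 14 = 77, and 77/91 = 85%.
- With the ±3-day infusion window, crossover falls on day +11 to +17, leaving 74 to 80 days (81–88%).

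**How much drug effect a late placebo value could carry.** The documents do not say, so these are assumptions.
- Dose-proportional: scheduled ETP doses at Weeks 54–64 sum to 0.1 + 0.3 + 0.3 + 0.6 + 0.6 + 1.0 = 2.9 mg/kg. The active arm before its Week 52 assessment has 10.9 mg/kg (Weeks 0–16) plus 17 × 3.0 (Weeks 18–50) = 61.9 mg/kg. 2.9 / 61.9 = 4.7%, taken as 5%.
- Time-proportional: (65 − 54) / 52 = 21%, rounded up to 25%.
- High side, spleen only: protocol section 4 reports a 25.3% decrease in 26 weeks in Phase 1b. Linear over 11 weeks this is 25.3 × 11/26 = 10.7 points, and 10.7/30 = 36% of the planned effect.

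**Shift in the placebo mean.** Let k late values join 16 evaluable placebo patients, each carrying fraction f of the effect. Shift = k/(16 + k) × f × effect. SE of the contrast = SD × √(1/16 + 1/(16 + k)).

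| Endpoint | k | SE | f = 5% | f = 25% | f = 36% |
|---|---|---|---|---|---|
| Spleen volume | 1 | 4.11 | 0.09 | 0.44 | 0.63 |
| Spleen volume | 2 | 4.05 | 0.17 | 0.83 | 1.19 |
| DLco | 1 | 6.97 | 0.07 | 0.37 | – |
| DLco | 2 | 6.87 | 0.14 | 0.69 | – |

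For f of 5–25% this is 0.02–0.21 SE for spleen volume and 0.01–0.10 SE for DLco. The high-side spleen case is 0.15–0.29 SE.

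**DLco power.** If the values stay missing (16 v 16), 92.8%. With late placebo values included:
- k = 1: 93.39% (f = 5%) and 92.85% (f = 25%).
- k = 2: 93.91% (f = 5%) and 92.91% (f = 25%).

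The added patients offset the dilution. If instead 1 or 2 active-arm patients carry 5–25% extra effect, the contrast rises by the same 0.07–0.69 (DLco) or 0.09–0.83 (spleen) points, and DLco power is 93.65–95.20%. Equal numbers and fractions in both arms cancel.

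**The case against.** The best defence is that the SAP as a whole makes the boundary clear. SAP 2.4.5 confines the comparison to the PAP and calls it 52 weeks. SAP 2.1.5 ends the PAP treatment epoch just before the first ETP infusion, and 2.4.4.1 ends PAP exposure at the first ETP dose. Section 2.6.4 is a general convention that also serves the PAP+ETP summaries, where the forward window does no such harm, and SAP 1.5 may be silent because no departure was intended. This shows what the authors probably meant, but it does not settle the matter. The epoch is a safety definition, the exposure rule is a duration calculation, and the scope statement is general. None of them overrides a specific, mandatory substitution rule.

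The second defence is rarity, and it stands. Protocol 6.2.1 counts a patient as having completed the PAP only after the Week 52 assessments. The schedule for Weeks 54–70 contains no MRI or PFT; the next are at Week 80. An affected patient must enter the ETP without a usable Week 52 value, then have an unscheduled test in Weeks 54–65 that is the closest qualifying value. The cutoff, a few days after the last patient finishes the PAP, narrows this further for late enrollees. It is also fair that the 85% is a share of calendar days and not a probability, and that the numbers affected are assumed.

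The rule in 2.4.5.1 on PFT values after the Week 38 infusion states no upper limit either. Its examples look back from Week 52, so it needs clarification only.

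**Conclusion.** The point holds and is minor. SAP 2.6.4 as written admits values from after the placebo arm has crossed over. For DLco and spleen volume that conflicts with protocol 11.5.2.1 and with the SAP's own scope statement; for liver volume, with the scope statement alone. With 1 or 2 placebo patients affected and 5–25% of the planned effect in each value, the shift is at most 0.69 points for DLco and 0.83 for spleen volume, or 1.19 for spleen volume on the high-side Phase 1b extrapolation. Power is not materially affected, and the net direction depends on which arm supplies the late values. The reason to act is that the rule fixing a primary endpoint value should agree with the protocol and not leave the choice to the programmer.

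**What to change.** Add to SAP 2.6.4: for the PAP analyses, a value used in place of a missing Week 52 value must have been taken before the patient's first ETP infusion and before any rescue; otherwise Week 52 stays missing and the MMRM handles it. State the same upper limit in the Week 38 rule of 2.4.5.1. Because SAP 2.6.3 analyses by nominal visit, apply the limit also to any late test recorded under Week 52. Worded this way, the sentence also covers the 45-day window for 3-monthly measures, which passes nominal Week 54 by 45 − 14 = 31 days.

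The cost is one sentence in each of two sections and the occasional late value not used. No in-window Week 52 assessment is lost: assessments are allowed at ±7 days, and the first ETP infusion is nominally no earlier than day +11.

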## 2.6.5 Pooling of centers for statistical analyses

Not applicable to the primary analysis. Investigation of the effects of geographic regions may be performed on an exploratory basis.

## 2.6.6 Statistical technical issues

A sensitivity analysis of the primary efficacy endpoints using a pattern mixture model and different imputations for values missing during the on-treatment period versus values missing after treatment discontinuation is planned. The description of the analysis refers to the DLco endpoint; differences in the implementation for the spleen volume and splenomegaly-related scores are noted. On-treatment period is defined as the time period between the start of first infusion of the study drug up to the day of last infusion in PAP +13 days for patients who did not continue in ETP, or up to the day before first infusion in ETP if the patient continued into ETP.

A pattern-mixture model sensitivity analysis of the percentage change in DLco (% predicted) from baseline to 52 weeks will be conducted, with a different imputation strategy applied for missing DLco values during the on-treatment period and missing DLco values after treatment discontinuation (ie, after the day of last infusion +13 days) based on the following assumptions:

- Patients within 13 days of their last IMP infusion would continue to show benefit from treatment similar to that observed at the scheduled time point. Therefore, DLco values missing during the on-treatment period will be considered “Missing At Random” and imputed using a model estimated using all samples collected on-treatment.
- Patients who stop taking their study treatment will no longer benefit from it in the future, and thus will tend to have DLco values returning to baseline. Thus DLco values missing after treatment discontinuation will be imputed based on a patient’s own baseline value.

Missing DLco values will be imputed 100 times to generate 100 complete data sets. The percent change from baseline to 52 weeks will be derived from observed and imputed DLco at this time point. The complete data sets will be analyzed using an ANCOVA model with treatment group, baseline DLco and baseline age as covariates. The results from the 100 analyses will be combined using Rubin’s formulae.

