8.1.6 Rescue treatment

If during the course of the study, a patient satisfies one or more of the following criteria indicative of clinical decline due to ASMD progression and after excluding other possible causes, study drug will be unblinded and the patient will be switched to the 3.0 mg/kg olipudase alfa group; dose escalating procedures and caveats provided in [Table 1](#) and [Section 8.1.3](#) will apply. See the study manual and the IXRS manual for unblinding procedures.

- Hemoglobin level falls below 7 g/dL and remains below 7 g/dL when hematology laboratory testing is repeated after approximately 2 weeks.
- Platelet count falls below 30 000/mm³ and remains below 30 000/mm³ when hematology laboratory testing is repeated after approximately 2 weeks.
- A clinically significant bleeding episode assessed by the investigator as related to a low platelet count.

These patients will continue to be followed in the study. Upon confirmation of the need for rescue treatment, patients will have organ volume MRI and PFTs performed if prior tests were performed more than 12 weeks before.

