### 1.1 STUDY DESIGN AND RANDOMIZATION

This Phase 2/3, multicenter, repeat-dose, clinical trial will be divided into 2 consecutive major periods: 1) a randomized placebo-controlled, double-blind PAP from Day -60 to Week 52 to be followed by 2) an ETP. Initially, the ETP will be double-blind as patients in the placebo arm cross over to active treatment. Study drug will be defined during the PAP as olipudase alfa or placebo, and during the ETP as olipudase alfa, and will be administered intravenously once every 2 weeks for 52 weeks in PAP, then for ETP. Day -60 to -1 is part of screening period with no study drug; some of the screening assessments which are not repeated right before the first infusion of study drug on Day 1 serve as baseline value for the study.

After completing the PAP, patients will enter the ETP of the study. Those who were randomized to the active arm will continue receiving the dose they were receiving at the completion of the PAP. Patients randomized to the placebo arm in the PAP will cross over to active treatment in the first infusion in ETP and will undergo dose escalation to a target dose of 3.0 mg/kg olipudase alfa.

For treatment periods during the PAP and the ETP, dose-limiting toxicity (DLT) criteria (protocol Section 8.1.4) and study stopping rules (protocol Section 8.1.5) will apply. If a patient satisfies protocol-specified criteria of rescue therapy (protocol Section 8.1.6), the individual treatment blind will be broken and the patient if on placebo will be switched to olipudase alfa; for patients already on olipudase alfa, the treatment will continue unless the patient drops out of study.

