## 1.4 STUDY PLAN

This Phase 2/3, multicenter, repeat-dose, clinical trial will be divided into 2 consecutive major periods: 1) a randomized placebo-controlled, double-blind PAP from Day -60 to Week 52, to be followed by 2) ETP for up to 4 years. Initially, the ETP will be double-blind as patients in the placebo arm cross over to active treatment, and the last patient completes PAP and when this patient is going through dose escalation the study is unblinded for analysis of PAP; ETP after unblinding for PAP analysis is open-label where all patients receive olipudase alfa.

The PAP will include a screening/baseline period and a treatment period. Approximately 36 patients who meet the eligibility criteria will be randomized in a 1:1 ratio across sites into 1 of 2 arms, placebo or 3.0 mg/kg olipudase alfa target dose. Patients will undergo a dose-escalation period to achieve the target dose level.

After completing the PAP, patients will enter the ETP. Patients randomized to the placebo arm in the PAP will cross over to active treatment in the ETP and will undergo dose escalation to a target dose of 3.0 mg/kg olipudase alfa. The patients who were randomized to the active arm will continue receiving olipudase alfa at the dose they complete PAP (with a mock dose escalation period to maintain blinding).

Study drug will be administered intravenously once every 2 weeks. In-patient hospitalization is required during dose escalation period and specific visits. Other infusions are administered at the clinic.

All patients will have an end of study/early discontinuation visit within 2 weeks after the last infusion of study treatment. In addition, all patients will receive a follow-up phone call for safety approximately 30 to 37 days after the last infusion of study drug.

A rescue strategy for patients who experience significant clinical decline (specific guidelines in the protocol, Section 8.1.6) will be in place: these individual patients may be unblinded and if receiving placebo, will be switched to olipudase alfa with proper dose escalation to a target dose of 3.0 mg/kg. These patients will continue to be followed to the end of study.

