### **2.3.2 Safety population**

The **safety population** is defined as a subset of the randomized population who received at least 1 infusion (partial or total), analyzed according to the treatment actually received during the PAP, irrespective of the treatment to which the patient has been randomized. For example, if a placebo patient was rescued to receive olipudase alfa in PAP, this patient will be counted as olipudase alfa treated patient. The safety population will not be changed after patients enter the ETP. Olipudase alfa infusions require special vials to be mixed with the vehicle while placebo infusions do not require these vials, and these vial numbers are called off by IXRS, it is unlikely that there will be any error in treatment received.

The **rescue population** is defined as patients who have used rescue strategy in PAP (ie, unblinded for treatment and continued on olipudase alfa irrespective of the randomized treatment assignment). Data after rescue in PAP will be provided separately for the rescue population.

In addition, nonrandomized but treated patients will not be part of the safety population; however, their safety data will be presented separately.

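### The pattern-mixture on-treatment period is not cut at rescue, so values excluded after rescue are imputed as missing at random in the analysis meant to test that assumption

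*SAP*

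**What the plan says.** SAP 2.4.5.1 fits the primary mixed model under MAR and leaves out measurements made after rescue starts. It then names the test of MAR: "To assess the robustness of the primary results to that assumption a pattern mixture model will be used". For patients who used rescue therapy, SAP 2.4.5 sets a general efficacy rule: "their data after rescue will NOT be included in the analysis".

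SAP 2.6.6 gives two imputation rules. A value missing in the on-treatment period is taken as MAR and imputed separately by treatment group. A value missing after treatment discontinuation is drawn around the patient's own baseline. The on-treatment period is "the time period between the start of first infusion of the study drug up to the day of last infusion in PAP" plus 13 days for a patient who does not enter the extension, or "up to the day before first infusion in ETP if the patient continued into ETP". Section 2.6.6 does not mention rescue.

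Rescue does not stop infusions. SAP 1.1 states: "Study drug will be defined during the PAP as olipudase alfa or placebo". Under SAP 1.4 a rescued patient, "if receiving placebo, will be switched to olipudase alfa with proper dose escalation to a target dose of 3.0 mg/kg". SAP 2.3.2 describes the rescue population as "unblinded for treatment and continued on olipudase alfa irrespective of the randomized treatment assignment". Protocol 8.1.6 ties rescue to "criteria indicative of clinical decline due to ASMD progression and after excluding other possible causes", judged by hemoglobin, platelet count or bleeding.

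**The concern.** Together these passages make post-rescue time on-treatment and make post-rescue values missing, so the MAR rule applies to them. The return-to-baseline rule is reached only when infusions stop, which rescue does not cause.

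Section 2.6.6 justifies MAR on the ground that a patient close to the last infusion keeps the benefit seen at the scheduled visit. A patient rescued for disease progression does not fit that reasoning. An olipudase-arm patient whose disease worsened enough for rescue could be given a typical treated patient's Week 52 value in both the primary analysis and the analysis meant to challenge it. Elsewhere the SAP does separate time before and after rescue: section 2.4.4.1 splits exposure there. The omission in 2.6.6 therefore looks like an oversight.

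**Working it through.** **1. The plan's own figure.** SAP 1.3 gives 36 patients randomized 1:1, 11% non-evaluable, a DLco difference of 25, SD 20, two-sided 5%, and power of 93%. Evaluable per arm: 18 × 0.89 = 16.02, taken as 16. The noncentrality is 25 / (20 × √(2/16)) = 3.54 on 30 degrees of freedom, which gives power 0.928. The stated figure reproduces, and it does not depend on the rescue rule.

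**2. Effect per patient when nothing informs the imputation.** The documents give no expected number of rescues, so r = 1 to 3 is an assumption, as is zero mean change on placebo. The comparison is between imputing r olipudase-arm patients at the arm mean and imputing them at baseline. The difference becomes d × (1 − r/18).

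| r | DLco, d = 25 | Spleen volume, d = 30 (size of reduction) |
|---|---|---|
| 0 | 25.0 | 30.0 |
| 1 | 23.6 | 28.3 |
| 2 | 22.2 | 26.7 |
| 3 | 20.8 | 25.0 |

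Each patient contributes 25/18 = 1.4 or 30/18 = 1.7 points. For scale, the plan's whole non-evaluable allowance is 18 × 0.11, about two patients per arm, so r = 3 already exceeds it.

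**3. Simulation for DLco.** Settings: 18 per arm, 50 imputations, Rubin's rules, 800 trials, unadjusted means, no Week 26 information. For r = 1, 2, 3 on olipudase, power was 0.96, 0.94, 0.93 under MAR and 0.93, 0.88, 0.84 under return to baseline. For r = 1, 2, 3 on placebo, the estimated difference was 25.0, 25.0, 25.4 under MAR and 25.3, 25.0, 24.9 under return to baseline. With no placebo change assumed, the two rules nearly agree in that arm.

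**4. What the plan conditions on.** The imputation model in SAP 2.6.6 includes baseline, age and the Week 26 value. Protocol 8.1.6 calls for organ-volume MRI and pulmonary function tests when rescue is confirmed, if the last ones are more than 12 weeks old. SAP 2.6.4 lets an unscheduled efficacy value within 91 days (13 weeks) fill a missing 6- or 12-month visit. A rescue-time value from about Week 26 − 13 = 13 can therefore stand for Week 26, and one from about Week 52 − 13 = 39 for Week 52. SAP 2.4.5.1 also uses a lung-function value taken after the Week 38 infusion as Week 52. The uninformed case in step 2 is thus mainly rescue before about Week 13.

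**5. Effect per patient with conditioning (illustrative).** Assume an arm mean of 15 at Week 26 and 25 at Week 52, a patient at 0 at Week 26, and equal SDs. The imputed mean is 25 + ρ × (0 − 15).

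- ρ = 0.5: 17.5, a shift of 17.5/18 = 1.0 point.
- ρ = 0.9: 11.5, a shift of 11.5/18 = 0.6 point.

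**The case against.** The strongest reply is that the plan already limits the problem. Rescue-time and Week 26 measurements enter the analysis (steps 4 and 5). SAP 2.4.5.1 also plans a mixed model that keeps post-rescue observations under the randomized arm, and a Wilcoxon-Mann-Whitney test that leaves rescued patients out. SAP 2.4.5.5 counts a missing Week 52 value as non-response. All of this stands, and a reader who inferred that the plan has no check on rescue would be wrong. But the first of these analyses uses the data instead of varying the missingness assumption, the second drops the patients, and the third is binary. None varies MAR for rescued patients on the primary scale.

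A second reply is that rescued olipudase patients may have nothing to impute. Protocol 11.5.2.1 excludes measurements after a switch of treatment, with placebo patients as its example, and SAP 1.1 says patients already on olipudase continue it. However, SAP 2.4.5 excludes post-rescue data for all patients who used rescue, and SAP 2.3.2 counts both arms in the rescue population. The SAP rule governs this analysis.

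Third, the return-to-baseline rule was justified for patients who stop treatment, and a baseline draw may be kind to someone who has fallen below baseline. That is fair: the draw is conservative relative to MAR for an olipudase patient but is not a worst case.

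Two stronger readings should be set aside. Section 2.6.6 read alone might suggest that olipudase values enter the placebo imputation model, but the general exclusion in 2.4.5 argues against this. Nor is rescue defined on the primary endpoints: its triggers are hematologic, so a link with DLco or spleen volume is plausible but not built in.

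**Conclusion.** The gap is real and narrow. Followed as written, the pattern-mixture analysis repeats the MAR assumption for values removed after rescue. It matters mainly for olipudase-arm patients rescued before the Week 38 infusion. The 1.4 DLco and 1.7 spleen-volume points per patient are an upper bound for the case with no informative pre-rescue value, and they assume zero placebo change. With a poor pre-rescue value the DLco shift is about 0.6 to 1.0 points under the assumptions in step 5. A total effect cannot be given because the documents state no rescue rate.

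A reader might infer that every rescued patient is imputed at the arm mean, or that the primary result is undermined. The documents support neither: the imputation is conditional, and only a sensitivity analysis is affected. Even with three uninformed rescues on olipudase, simulated DLco power is 0.84.

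**What to change.** For this sensitivity analysis only:

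- In SAP 2.6.6, end the on-treatment period at the earlier of its present end point (last infusion + 13 days, or the day before the first extension infusion) and the first rescue infusion.
- State that post-rescue values are kept out of DATAIN, the input to the imputation model.
- Where no pre-rescue value qualifies as Week 52 under SAP 2.4.5.1 or 2.6.4, impute Week 52 for rescued patients with the return-to-baseline draw already specified in 2.6.6. Label it a conservative non-MAR assumption.

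The cost is one revised definition and minor code. The downside is a slightly less favorable sensitivity estimate if olipudase patients are rescued early. The primary analysis and the clinical rescue rule are unchanged.
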